6.2.3 Storage and processing

The stem cells are processed in the Duke University Medical Center Stem Cell Laboratory and infused to the donor following the standard laboratory procedures for allogeneic stem cell infusions. Freshly collected cells will be used in the first course of treatment and donor cells will be divided into aliquots and cryopreserved in liquid nitrogen for subsequent infusions. Each infusion of the cells will be performed 1 day following each chemotherapy regimen and that day will be counted as 'day 0'. The target dose of CD3+ cells is 1×10^8 cells/kg (the collection goal of 3×10^8 CD3+ cells/kg is to obtain 1 aliquot of 1×10^8 CD3+ cell/kg for each of induction and consolidation2, with 1×10^8 CD3+ cell/kg saved in case of need for re-induction). If only $2-3 \times 10^8$ CD3+ cell/kg is collected, then cells will only be given with IND1 and CON2 (IND2 may still be done, but cells will not be given). We will also monitor the total number of mononuclear, CD34+, CD3-CD16+CD56+ (NK) cells, CD3+CD16+CD56+ (NKT) cells, and gamma-delta T-cells infused, but the infusion dose will be calculated around CD3+ population.

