6.3 Treatment Plan

6.3.1 Induction therapy

Eligible subjects will receive induction chemotherapy with idarubicin (12 mg/m^2 intravenously for 3 days) and cytarabine (100 mg/m^2 intravenously for 7 days) starting Day 1 and ending Day 7 as described in Figure 1. Patients 80 years or older may receive 2 and 5 days of idarubicin and cytarabine respectively starting Day 1 and ending Day 5 (optional, at physician discretion). HLA-mismatched DLI will be administered Day 9

Chemo with Adoptive Haplo DLI

(DLI will occur on Day 7 for 5+2 regimen), approximately 24-48 hours following completion of chemotherapy at a dose of 1×10^8 CD3+ cells; however, due to logistics of planning infusions with staffing, donor availability, weekends/holidays, etc., it may be necessary to postpone cell infusion up to 96 hours, which will be allowed without being considered a protocol violation.

Subjects who experience no remission or partial remission will receive a second course of the identical induction chemotherapy (IND2). IND2 should include 7+3+DLI as per IND1, but if cells are not available as per 6.2.3, chemotherapy alone can be given without being considered a protocol violation.

Given the time constraints presented by the need to start induction chemotherapy as soon as possible, in some cases, it may not be logistically possible to administer cells with induction (e.g., obtaining insurance approval for clinical trial/DLI may take a while, and approval may not be back in time for a patient to receive cells). In these cases, patients would just receive standard induction chemotherapy and cells would be administered after CON1 in addition to CON2 (see below). Timing of correlative laboratory studies will be adjusted to match cell infusion. Guo et al. have reported improved outcomes with high cell doses (1×10^8 CD3+ cells/kg) administered after consolidation, even in patients who receive standard induction chemotherapy without cells.¹

¹Guo M, Hu KX, Liu GX, Yu CL, Qiao JH, Sun QY, Qiao JX, Dong Z, Sun WJ, Sun XD, Zuo HL, Man QH, Liu ZQ, Liu TQ, Zhao HX, Huang YJ, Wei L, Liu B, Wang J, Shen XL, Ai HS. HLA-mismatched stem-cell microtransplantation as postremission therapy for acute myeloid leukemia: long-term follow-up. *J Clin Oncol.* 2012 Nov 20;30(33):4084-90. doi: 10.1200/JCO.2012.42.0281. Epub 2012 Oct 8.

[figure not shown]

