6.3.2 Postremission treatment

Subjects who achieve a CR will receive 2 further courses of cytarabine postremission chemotherapy (consolidation) at 1.0 g/m^2 for 6 dosages followed by HLA-mismatched DLI after the second consolidation. Cytarabine will be given twice daily at 12 hour intervals on days 1, 3, and 5; HLA-mismatched DLI will be administered the day following the completion of the second consolidation (day 7) at a dose of $1 \times 10^8 \text{ CD3+ cells}$, although as above, a 24-96 hour interval between completion of chemotherapy and infusion of cells will be allowed for logistical reasons without being considered a protocol violation.

No cells will be given after the first consolidation, as chemotherapy given with the second consolidation will likely kill any cells infused after the first consolidation (i.e. infusion of cells after the first consolidation would be costly and low-yield) (Note that while this argument could also be applied to cells infused after induction, Guo et al. showed an improvement in the CR rate from 40% to 80% with the use of cells with induction, which is why we plan to use cells after induction in this trial).

The timing of consolidation typically takes place after count recovery, around 6-12 weeks after induction, following standard protocols and timing for cytarabine consolidation.

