11.0 STUDY DESIGN AND ANALYSIS

11.1 Primary Objectives:

10.1.1 Safety: Evaluate the safety of HLA-haploidentical DLI combined with conventional induction and consolidation chemotherapy in terms of unacceptable toxicity as defined in section 7.0.

A maximum of 30 subjects will be consented for a maximum of 21 evaluable subjects accrued to this protocol over a period of 2 years. Safety will be evaluated by the number of subjects with unacceptable toxicity as defined by any of the following:

- i. Grade III or IV aGVHD of the gut or liver or Grade IV aGVHD of the skin lasting > 7 days;
- ii. Grade IV CTCAE toxicity attributable to DLI (e.g. infusion reaction, as opposed to Grade IV CTCAE toxicity from chemotherapy) and lasting >7 days
- iii. Treatment-related mortality (TRM), keeping in mind that anticipated mortality from standard induction chemotherapy in the elderly ranges from 11% for subjects 55-65 years-old with ECOG 0 to 50% for subjects older than 75 years with ECOG 2 [1].

Simon's optimal two stage design will be applied. These rules permit the study to be closed early if there is evidence that the true unacceptable toxicity rate is ≥ 0.40 . The stopping rules in the table below will also allow us to test the null hypothesis that the true toxicity rate is ≥ 0.40 against the alternative hypothesis that the true toxicity rate is ≤ 0.20 . The Type I and II error rates for this design are 0.15 and 0.2, respectively. Given that the true toxicity rate is 0.40 (0.20), the probability of stopping the trial at Stage 1 to accept the null hypothesis is 0.7 (0.16). The significance level of this design is 0.15 and the power is 0.80.

| Stage | Total Accrual | Close study/therapy if number of subjects with unacceptable toxicity is \geq |
|-------|---------------|--|
| 1 | 11 | 4 (45%) |
| 2 | 21 | 7 (33%) |

Rates of unacceptable toxicity will be calculated and monitored with the stopping rules in the table above. Toxicity in the other categories will be informally monitored and tabulated by Type and Grade, but they will not be used to determine tolerability of the procedure.

Chemo with Adoptive Haplo DLI

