For purposes of toxicity monitoring, each patient will be followed for unacceptable toxicity until a toxic event occurs or until 8 weeks after last cell infusion, whichever comes first. Accrual will not be suspended while collecting data for the interim analyses. However, as soon as a boundary within a stage in the table above is crossed, the study will be closed to further accrual. This design and the above boundaries will constitute our stopping rules for safety.

11.1.2 Efficacy: Evaluate the efficacy of HLA-haploidential DLI infusion combined with conventional induction and consolidation chemotherapy in terms of donor-recipient chimerism and microchimerism.

The assessment of efficacy will be conducted after collecting data for a maximum of 21 evaluable subjects. Our primary efficacy endpoint is the 1-year DFS rate following adoptive transfer. Using the chi-square test, we will test the null hypothesis is the CR rate will be ≤ 0.20 against the true hypothesis that 1-year DFS rate is >0.45 . With 21 patients, we can test this with approximately 84% power with one-sided alpha level of 0.05. Additional efficacy endpoints include the CR rate, overall response rate (CR + partial response), OS, and count recovery. CR and overall response rates will be calculated with one-sided 90% confidence interval. DFS and OS will be estimated using the method of Kaplan and Meier. All statistical analyses will be conducted in conjunction with our co-investigator, [name]., Assistant Professor of Biostatistics and Bioinformatics.

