| PD1/PDL1/PDL2 expression (Research) | X | | X | At 8 weeks after last therapy | X |
| Cytokine Release Syndrome (Research) | | To be drawn before infusion and 2 days after infusion for IND1, IND2, and CON2 as applicable | | | |
| Toxicity monitoring (Grade 3-4) (Epic) | | Daily | Qo wk | Qo wk till 8 weeks after last therapy and then q 4 weeks for 12 more weeks | |
| Acute GVHD monitoring (Epic) | | Daily | Qo wk | Qo wk till 8 weeks after last therapy and then q 4 weeks for 12 more weeks | |

¹ Tests at entry are recommended to be done within 1 week before initiating therapy; however if there are no sig. change in patient's status and tests are less than 4 weeks old then they are acceptable; exceptions include bone marrow aspirate and biopsy and cardiopulmonary testing (acceptable if within 8 weeks)

² Therapy and recovery refer to the period while the patient is receiving induction (IND1 or IND2) or consolidation chemotherapy until count recovery and discharge

³ For cardiopulmonary testing, refer to section 5.1.

⁴If patient already had a bone marrow biopsy and this was not collected, ok to skip

⁵ Per investigator discretion

⁶ Count Recovery would be considered when the ANC count is >1000/uL

⁷ If any subjects do not complete all the therapies (i.e. Induction 1/2, Consolidation 1 and 2), they will be followed for survival, but do not need to complete any listed assessments

⁸Any leftover cells at q3months after completing therapy will be used to run NK Lysis, TCR sequencing, and PD1/PDL1/PDL2 expression research samples. Additional blood will not be drawn for this testing.

*Other labs may be performed/followed per institutional policy

II. DONOR SCHEDULE OF EVENTS TABLE

| Test | At Entry |
|---|----------|
| History, physical (Epic) | X |
| ABC / DIFF, Serum BUN/Cr/CA/MG/PO/AST/ALT/Bili/TP/ALB/K/NA /CL/CO3/Glu/CMV viral titre (Epic) | X |
| Serum quantitative Beta-HCG for females (Epic) | X |
| CXR (AP/lateral), EKG (12 lead) (Epic) | X |
| FACT labs* (Epic) | X |
| KIR typing (Research) | X |
| Microchimerism (Research) | |
| TCR sequencing (Research) | X |

*See appendix for standard FACT (Foundation for Accreditation of Cellular Therapy) labs. FACT labs must be drawn and final test results available within 7 days prior to infusion into the patient.

III. GVHD Grading Criteria

| GvHD | | | | | | |
|--------------------|----------------------------------|----------|--|--|-------------------------------|---|

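### The safety stopping rule's toxicity window is tied to an undefined last cell infusion, so a treatment-related death in the cell-free first consolidation may go uncounted

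*Combined protocol and SAP*

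**What the plan says.** Section 11.1 (Safety) sets the period over which events feed the two-stage stopping rule: "each patient will be followed for unacceptable toxicity until a toxic event occurs or until 8 weeks after last cell infusion, whichever comes first". The rule closes the study at 4 or more subjects with unacceptable toxicity out of 11, or 7 or more out of 21. Criterion iii of the toxicity definition is treatment-related mortality. Unlike criterion ii, it is not limited to events attributed to the donor cells. The primary safety objective covers the cells together with induction and consolidation chemotherapy.

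The treatment schedule is in sections 6.2 and 6.3:

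- Induction (7+3), section 6.3.1: "HLA-mismatched DLI will be administered Day 9". For 5+2 the infusion is on Day 7. A delay of up to 96 hours after chemotherapy is allowed.
- CON1, section 6.3.2: "No cells will be given after the first consolidation".
- Consolidation timing, section 6.3.2: "The timing of consolidation typically takes place after count recovery, around 6-12 weeks after induction".
- Short collection, section 6.2.3: "then cells will only be given with IND1 and CON2 (IND2 may still be done, but cells will not be given".
- No cells available at induction, section 6.3.1: "patients would just receive standard induction chemotherapy and cells would be administered after CON1 in addition to CON2".

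Appendix I uses a different anchor. Toxicity and acute GVHD are monitored daily during therapy and recovery, consolidation included, and afterwards "Qo wk till 8 weeks after last therapy and then q 4 weeks for 12 more weeks". Footnote 7 of the same table releases subjects who do not complete all therapies from every listed assessment, leaving only survival follow-up. Section 9.0 has a third clock: all serious adverse events to 30 days after the last infusion, and after that only those thought related to treatment.

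**The concern.** The window hangs on an infusion that some subjects never reach. A subject who dies in CON1 does not get the CON2 infusion that would have moved the end of the window later. If the last infusion received is the anchor, the death itself fixes the early end of the window and may then lie beyond it. A subject who stops before CON2 has the same exposure for later grade IV toxicity attributed to the cells, severe acute GVHD or treatment-related death.

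The boundaries are small integers and they bind. One event left out at a boundary (4 read as 3 of 11, or 7 read as 6 of 21) removes the stop. Two people applying section 11.1 to the same CON1 death could reach different counts, one reading the anchor as received and the other as planned.

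**Working it through.** **1. Reproduce the plan's design.** Inputs from section 11.1: n1 = 11, stop if X1 ≥ 4; n = 21, reject if X1 + X2 ≥ 7; rates 0.40 (null) and 0.20 (alternative).

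- Stage 1 stop = P(X1 ≥ 4), with X1 ~ Bin(11, p).
- Declare acceptable = sum over x = 0 to 3 of P(X1 = x) × P(X2 ≤ 6 − x), with X2 ~ Bin(10, p).

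At p = 0.40: 0.0036×0.9452 + 0.0266×0.8338 + 0.0887×0.6331 + 0.1774×0.3823 = 0.150.

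| p | Stage 1 stop | Declare acceptable | Plan states |
|---|---|---|---|
| 0.40 | 0.704 | 0.150 | 0.7 and 0.15 |
| 0.20 | 0.161 | 0.801 | 0.16 and 0.80 |

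The plan's figures are reproduced. The Stage 1 boundary is printed with 45%, but 4/11 is 36%. A boundary of 5 of 11 would give a Stage 1 stop of 0.467 at p = 0.40, so 4 is the operative number.

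**2. When the window closes if the induction infusion is the last received.** Close = infusion day + 56.

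- 7+3: 9 + 56 = Day 65.
- 7+3 with the full 96-hour delay: 7 + 4 = Day 11, and 11 + 56 = Day 67.
- 5+2: 7 + 56 = Day 63.

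**3. When CON1 starts.** Section 6.3.2 gives 6 to 12 weeks after induction and does not say whether this runs from its start (Day 1) or its end (Day 7 for 7+3). Both are shown, against a Day 65 close.

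| Interval | CON1 day 1 (from start / from end) | Days from CON1 day 1 to close |
|---|---|---|
| 6 weeks | Day 43 / 49 | 22 / 16 |
| 8 weeks | Day 57 / 63 | 8 / 2 |
| 12 weeks | Day 85 / 91 | −20 / −26 (closed before CON1) |

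Part or all of CON1 and its recovery lies outside the window. No CON1-to-CON2 interval is given. Even with CON1 at Day 43, CON2 would have to begin within 65 − 43 = 22 days of CON1 to start inside the window, so CON2 before cells is probably outside.

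**4. Second induction.** If IND2 is given without cells, the window still runs from the IND1 infusion and CON1 moves later. If IND2 includes cells, the window runs from that infusion and a similar gap can follow.

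**5. Effect on the rule.** The documents give no toxicity or mortality rate for consolidation, so the uncounted amount is assumed. At a true rate of 0.40:

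| Points uncounted (assumed) | Counted rate | Stage 1 stop | Declare acceptable |
|---|---|---|---|
| 0 | 0.40 | 0.704 | 0.150 |
| 2 | 0.38 | 0.655 | 0.194 |
| 5 | 0.35 | 0.574 | 0.276 |

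**6. Cost of widening the window with boundaries unchanged.** If 2 points are added to a true 0.20 (assumed), the counted rate is 0.22, power falls from 0.801 to 0.738 and the Stage 1 stop rises from 0.161 to 0.208. If 5 points are added (0.25), power is 0.632 and the Stage 1 stop 0.287.

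**The case against.** The strongest reply is that a subject in CON1 is still on protocol, is awaiting planned CON2 cells and is under daily toxicity monitoring. On Day 65 nobody can know that the induction infusion was the last. Read prospectively, follow-up is still open when the death occurs, and it counts. That reading is possible, but section 11.1 does not state it, and for a subject who dies in CON1 the planned infusion never takes place. What stands is that undercounting follows from one of two readings. A reader might infer that the count is certainly biased downward; the text supports only that it can be.

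Other limits also stand:

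- Only subjects in complete remission reach CON1, criterion ii excludes chemotherapy toxicity, and the mortality figures in the plan are for induction. The uncounted share may be small.
- Nothing says that the 0.40 and 0.20 rates were set for a wider window.
- Related serious adverse events are reported for the whole study, so a related CON1 death would be known. The gap is in what the rule counts, since nothing links those reports to it.

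A reader might also infer that CON2 before cells always lies outside the window. It does not on the delayed-cell route, where cells follow CON1 and can cover CON2, and the timing after IND2 with cells is not given. Nor is an induction death on the delayed-cell route shown to be lost. With no infusion the 8-week limb has no date and cuts nothing off; what is missing is an end point and a statement on evaluability.

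**Conclusion.** The point holds as an ambiguity with a likely direction. On the standard route, if the anchor is the last infusion received, the window closes about Day 65 (Day 63 for 5+2, Day 67 with the full delay). A treatment-related death later in CON1, and probably in CON2 before cells, then meets criterion iii without entering the count. Events early in CON1 and deaths unrelated to treatment are unaffected.

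The size cannot be fixed from the documents. The increases in false acceptance, to 0.194 and 0.276, rest on assumed losses of 2 and 5 percentage points at a true rate of 0.40 and show sensitivity only. Larger losses could be put through the same formula, but nothing in the plan anchors them. The change is worth making because the rule is binding, the counts are small and the repair is short.

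**What to change.** In section 11.1, run the counting window for the stopping rule continuously from the first protocol treatment to 8 weeks after the last protocol treatment actually received, chemotherapy or cells. State that events in CON1 and in CON2 before cells count.

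Reconcile this with Appendix I, which already follows subjects from the last therapy, and say whether events in its further 12 weeks enter the count or are descriptive only. Say how related serious adverse events reported under section 9.0 feed the count. Amend footnote 7 so that subjects who stop early keep toxicity and acute GVHD monitoring to the end of the counting window. It might be supposed that wording alone is enough because Appendix I already schedules the visits, but footnote 7 removes them for these subjects. State whether a subject who never receives cells is evaluable for safety.

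The cost is protocol wording, some added follow-up for those who stop early, and a higher counted rate against unchanged boundaries. The last lowers power, for example from 0.80 to 0.74 if 2 points are added to a true 0.20 (assumed). The sponsor should therefore confirm that 0.40 and 0.20 are the intended rates for the wider window.

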2.0 STUDY OBJECTIVES

2.1 Primary Objective

2.1.1 Evaluate the safety of HLA-haploididentical DLI combined with conventional induction and consolidation chemotherapy in terms of unacceptable toxicity as defined in section 7.0.

2.1.2 Evaluate the efficacy of HLA-haploidentical DLI combined with conventional induction and consolidation chemotherapy in terms of one-year DFS.

2.1.3 Validate the use of the CGA in elderly AML and MDS patients undergoing cellular therapy

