7.0 EVALUATION CRITERIA AND DEFINITIONS

1. Standardized response criteria will be used following **National Comprehensive Cancer Network (NCCN)** recommendations found on the NCCN website: www.nccn.org.
2. GVHD will be graded with standard criteria (see Appendix II). Other toxicity will be graded as per the NCI Common Terminology Criteria for Adverse Events (CTCAE) version 4.0 (see Appendix III). Grade 3-4 will be reported.
3. Unacceptable toxicity will be defined as either:
 - a. Grade III or IV aGVHD of the gut or liver or Grade IV aGVHD of the skin lasting > 7 days;

Chemo with Adoptive Haplo DLI

- b. Other grade IV CTCAE toxicity attributable to the DLI (e.g. infusion reaction, and distinct from grade IV toxicity attributable to chemotherapy) and lasting > 7 days
 - c. Treatment-related mortality (TRM), keeping in mind that anticipated mortality from standard induction chemotherapy in the elderly ranges from 11% for subjects 55-65 years-old with ECOG 0 to 50% for subjects older than 75 years with ECOG 2 [1].
4. Disease-free survival (DFS) is the time from CR to relapse or death.
5. Overall survival (OS) is the time from start of therapy to either death or the last day of follow-up for that patient.
6. Event Free Survival (EFS) is the time from start of therapy to progression of AML or relapse or death.
7. Neutrophil recovery time is defined as the first of 3 consecutive days in which the ANC is $>0.5 \times 10^9/L$
8. Platelet recovery is defined as the first of 3 consecutive days in which the platelet count is $>20 \times 10^9/L$
9. PD1/PDL1/PDL2 expression (marker of T cell exhaustion)
- 10.

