12.0 ANTICIPATED TOXICITY OF DLI PROCEDURE

12.1 GVHD

Although GVHD is a common complication of DLI, given the absence of GVHD in a similar study by Guo et al.[6], we do not anticipate any GVHD in our study. This is because unlike a traditional transplant in which that patient engrafts with donor cells, which then go on to cause GVHD, we do not expect long-term engraftment, and therefore donor cells should not persist long enough to cause GVHD.

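### Section 11.1.2 words primary efficacy as chimerism and dates the DFS year from cell infusion, in conflict with 2.1.2, 7.0 and its own endpoint sentence

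*Combined protocol and SAP*

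**What the plan says.** **The objective.** Section 2.1.2 sets the primary efficacy objective for DLI with "conventional induction and consolidation chemotherapy in terms of one-year DFS". Section 11.1.2, which is meant to carry that objective into the analysis, words it as DLI with "conventional induction and consolidation chemotherapy in terms of donor-recipient chimerism and microchimerism". The next paragraph of 11.1.2 returns to DFS: "Our primary efficacy endpoint is the 1-year DFS rate following adoptive transfer". The only efficacy test, alpha, power and sample size in the section belong to that endpoint. Elsewhere chimerism is a monitored item under immune recovery (11.2.4, item 7) and a subgroup factor (11.3).

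**The clock.** Section 7.0, item 4, gives the origin: "Disease-free survival (DFS) is the time from CR to relapse or death". Section 11.1.2 dates the year from adoptive transfer. Under 6.3.1 and 6.3.2, cells are given on Day 9 of first induction (Day 7 for the shortened regimen), possibly with a second induction, and after second consolidation. Where cells cannot be arranged in time for induction, they are given after first consolidation as well as second. No section says which infusion starts the year.

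**The concern.** A primary endpoint needs one variable, one time origin and one set of subjects. Section 11.1.2 gives two variables for the same objective and an origin that differs from the plan's own definition of DFS.

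The origin matters in different ways for two groups. Subjects given cells at induction would start the clock before CR has been assessed, so their year ends a few weeks early on the 7.0 scale. Delayed subjects would start it after CR. Any of them who relapsed or died between CR and first cells would have no start date and would be missing from the primary DFS rate. A single rate in 21 subjects would then mix clocks that begin on either side of remission.

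A further gap appears once the origin is fixed. With DFS counted from CR, subjects who never reach CR have no DFS time, and 11.1.2 does not say how they enter the rate.

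**Working it through.** **1. The plan's own figure.** Inputs from 11.1.2: n = 21, p0 = 0.20, p1 = 0.45, one-sided alpha 0.05. Both rates are read here as one-year DFS rates, although the text sets "the null hypothesis is the CR rate will be ≤ 0.20" against "the true hypothesis that 1-year DFS rate is >0.45".

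Power = Φ{[√n (p1 − p0) − 1.645 √(p0(1 − p0))] / √(p1(1 − p1))}
= Φ{[4.583 × 0.25 − 1.645 × 0.400] / 0.4975} = Φ(0.98) = 0.837.

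The stated 84% reproduces. The exact binomial rule (reject at 8 or more of 21) has alpha 0.043 and power 0.803. The power figure is not in dispute.

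**2. Distance between the two origins.**
- CR is assessed at hematologic recovery, 4-6 weeks (Appendix I). Counted from Day 1 (an assumption), that is Day 28-42.
- Cells at induction: Day 9, so 28 − 9 = 19 to 42 − 9 = 33 days before CR, about 3-5 weeks.
- Cells after first consolidation: consolidation starts about 6-12 weeks after induction (6.3.2), and cells follow about a week later, so about 7-13 weeks. Relative to CR this is 7 − 6 = 1 to 13 − 4 = 9 weeks later. The range pairs extreme timings.

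**3. Subjects given cells at induction.** Assume a constant hazard and true one-year DFS from CR of 0.20. A year from Day 9 ends 52 − 5 = 47 to 52 − 3 = 49 weeks after CR:
- 0.20^(47/52) = 0.233
- 0.20^(49/52) = 0.220

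Among those who reach CR the rate reads 0.22-0.23 instead of 0.20, a shift of about 2-3 points. The gap is longer for subjects who need a second induction.

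**4. Delayed subjects.** Same assumptions. The share of CR subjects who relapse or die before first cells is:
- 1 − 0.20^(1/52) = 0.03
- 1 − 0.20^(9/52) = 0.24

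This is the share left out, not the bias in the rate. With a constant hazard, those who do start the clock still have 0.20^((t + 52)/52) / 0.20^(t/52) = 0.20. The rate itself rises only if the relapse hazard falls with time since CR.

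**5. The denominator under a CR origin.** Section 3.1 gives CR rates of about 30-65% with standard induction. Then 21 × 0.30 = 6.3 and 21 × 0.65 = 13.65, so about 6-14 subjects have a DFS time. The formula in step 1 gives:
- n = 6: Φ(−0.09) = 0.46 (exact 0.26)
- n = 14: Φ(0.56) = 0.71 (exact 0.66)

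At the 80% CR rate of the pilot study in section 3.7 (17 subjects), power is 0.77 (exact 0.71).

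If all 21 are kept and subjects never in CR count as failures, N stays at 21. The rates 0.20 and 0.45 must then be read over all 21. With 65% in CR, an overall rate of 0.45 needs 0.45/0.65 = 0.69 among CR subjects; with 80%, 0.45/0.80 = 0.56; with 30%, it cannot be reached.

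**The case against.** The strongest reply is that the chimerism phrase is a stray. Section 2.1.2 and the body of 11.1.2 both name one-year DFS, and every design figure belongs to it. That stands. A reader might infer that the trial could claim efficacy on microchimerism, but the documents give no criterion for it to meet.

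A reader might also take section 12.1, where "we do not expect long-term engraftment", as proof that chimerism cannot mark benefit. That does not follow. Section 1.0 separates the two: in the pilot study no patient had full or mixed chimerism, yet donor microchimerism was found in all four women with male donors.

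On the clock, 2.1.2 gives no origin, and the legend to Figure 1 uses adoptive transfer as a name for the cell treatment. The endpoint sentence might therefore mean only DFS after this therapy, with 7.0 supplying the origin. The reading is possible, but a primary endpoint should not depend on it.

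Finally, a reader might infer that relapses before first cells are lost to the trial. They are not: EFS and OS run from start of therapy (7.0) and are planned analyses (11.2.3). The loss is confined to the primary DFS rate.

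**Conclusion.** The point holds as a contradiction in the primary endpoint that should be corrected before analysis. Section 11.1.2 disagrees with 2.1.2 and with itself on the variable, and with 7.0 on the origin.

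The numerical effect is modest where it can be sized: about 2-3 points for subjects given cells at induction. Among delayed subjects in CR, about 3-24% would be left out of the primary rate. Both figures assume a constant hazard, one-year DFS of 0.20 and the timings in step 2. The documents call delay something that happens in some cases and give no number, so no effect on the overall rate in 21 subjects can be stated.

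The denominator is potentially the larger matter. Restricting the analysis to CR subjects would take power from the stated 84% to about 0.46-0.71 (normal approximation), if the 30-65% CR range applies. This gap already exists under 7.0, and settling the origin without settling the denominator would leave it open.

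**What to change.** In section 11.1.2:

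1. Word the objective in terms of one-year DFS, as 2.1.2 does, and leave chimerism and microchimerism as correlatives under 11.2.4.
2. Remove the reference to adoptive transfer from the endpoint sentence and use the date of CR, as in 7.0. State that relapse or death before first cells in delayed subjects counts as an event.
3. State the denominator. One option is all 21 evaluable subjects, with those who never reach CR counted as failures. This keeps the N behind the 84%, provided 0.20 and 0.45 are justified as rates over all 21. If only CR subjects are analysed, restate the power.
4. In the same edit, name the same quantity in the null and the alternative, since the null is now labelled a CR rate.

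No new data are needed. The cost is more than a change of wording: section 11.1 does not define evaluable, so items 2 and 3 settle who is analysed, and the 0.20 and 0.45 may need a fresh justification. The reported rate may also be lower, because early relapses in delayed subjects, and subjects never in CR under the option in item 3, would count as failures.

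### The chi-square test planned for 1-year DFS holds its one-sided 0.05 level at n = 21 (with exact power about 80%, not 84%) but not at several smaller sizes the plan allows; an exact binomial test should be named

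*Combined protocol and SAP*

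**What the plan says.** Section 11.1.2 names 1-year DFS as the primary efficacy endpoint and gives the method as "Using the chi-square test, we will test the null hypothesis". The null is worded as "the CR rate will be ≤ 0.20" and the alternative as "1-year DFS rate is >0.45", with a "one-sided alpha level of 0.05". The operating characteristic is given for one size: "With 21 patients, we can test this with approximately 84% power". No continuity correction, exact method, critical count or rule for a smaller number is stated.

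The number analysed is capped, not fixed: "The assessment of efficacy will be conducted after collecting data for a maximum of 21 evaluable subjects". The safety part of Section 11.1 sets the matching accrual limit: "A maximum of 30 subjects will be consented for a maximum of 21 evaluable subjects". It also closes accrual once a toxicity boundary is crossed, with boundaries tabulated at 11 and 21 subjects. Section 7.0, item 4, defines the endpoint: "Disease-free survival (DFS) is the time from CR to relapse or death".

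**The concern.** The chi-square test relies on a large-sample approximation. Under the null the expected number of successes is 0.20 × 21 = 4.2 at the maximum size, and fewer below it. With counts this small, the true level jumps up and down from one n to the next and need not stay under 0.05. The plan quotes its level and power only at n = 21, but allows the analysis to run on fewer subjects.

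The documents give three ways for that to happen: a shortfall in evaluable subjects, early closure for toxicity, or a DFS rate computed only in subjects who reach CR. At stake is whether a positive result on a primary objective (Section 2.1.2) carries the false-positive rate the plan states.

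**Working it through.** **Inputs.** p0 = 0.20, p1 = 0.45, one-sided 0.05, maximum n = 21 and stated power of about 84%, all from Section 11.1.2. The two rates are treated as values of a single binary endpoint, with one-year status known for every subject analysed.

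**Step 1: reproduce the stated power.** The uncorrected one-sample normal (score, or chi-square) formula is

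Power = Φ{ [(p1 − p0)√n − 1.645·√(p0(1 − p0))] / √(p1(1 − p1)) }.

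At n = 21 this is Φ{ [0.25 × 4.583 − 1.645 × 0.400] / 0.4975 } = Φ(0.980) = 0.8365, the plan's 84%. Other forms give:
- continuity-corrected: 0.777
- two-sided: 0.766
- arcsine: 0.801
- alternative variance only: 0.745
- null variance only: 0.889
- exact binomial: 0.803

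Only the uncorrected one-sided form comes within two points of 84%, so that is the fair reading of the test.

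**Step 2: the rule at n = 21.** Reject at the smallest r with (r − 0.2n)/√(0.16n) ≥ 1.645. For r = 7 the statistic is (7 − 4.2)/1.833 = 1.53. For r = 8 it is (8 − 4.2)/1.833 = 2.07. The cut-off is therefore 8. Exact binomial tails give P(X ≥ 8 | 0.20) = 0.0431 and P(X ≥ 8 | 0.45) = 0.8029. The exact test also has cut-off 8, because P(X ≥ 7 | 0.20) = 0.1085.

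**Step 3: the same rule at smaller n.** One subject fewer moves the cut-off: at n = 20, (7 − 4)/1.789 = 1.677, so 7 successes now reject. The exact rule takes the smallest r with P(X ≥ r | 0.20) ≤ 0.05. All levels and powers below are exact binomial tails.

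| n | Chi-square: reject at ≥ | Level | Power | Exact: reject at ≥ | Level | Power |
|---|---|---|---|---|---|---|
| 10 | 5 | 0.0328 | 0.496 | 5 | 0.0328 | 0.496 |
| 11 | 5 | 0.0504 | 0.603 | 6 | 0.0117 | 0.367 |
| 12 | 5 | 0.0726 | 0.696 | 6 | 0.0194 | 0.473 |
| 13 | 5 | 0.0991 | 0.772 | 6 | 0.0300 | 0.573 |
| 14 | 6 | 0.0439 | 0.663 | 6 | 0.0439 | 0.663 |
| 15 | 6 | 0.0611 | 0.739 | 7 | 0.0181 | 0.548 |
| 16 | 6 | 0.0817 | 0.802 | 7 | 0.0267 | 0.634 |
| 17 | 7 | 0.0377 | 0.710 | 7 | 0.0377 | 0.710 |
| 18 | 7 | 0.0513 | 0.774 | 8 | 0.0163 | 0.609 |
| 19 | 7 | 0.0676 | 0.827 | 8 | 0.0233 | 0.683 |
| 20 | 7 | 0.0867 | 0.870 | 8 | 0.0321 | 0.748 |
| 21 | 8 | 0.0431 | 0.803 | 8 | 0.0431 | 0.803 |

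Averaged with equal weight over n = 11 to 21, the chi-square level is 0.6952/11 = 0.063.

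**Step 4: which sizes could occur.**
- Early closure: Section 11.1 puts the chance of stopping at stage 1 at 0.16 if the true toxicity rate is 0.20, and 0.7 if it is 0.40. Accrual continues while interim data are collected, so the final number after closure is not fixed.
- CR-only denominator: the 30–65% CR range in Section 3.1 gives 21 × 0.30 = 6.3 to 21 × 0.65 = 13.7 subjects. The 80% reported for the cell-infusion arm in Section 3.7 gives 21 × 0.80 = 16.8. Below n = 10 the pattern is equally uneven: 0.099 at n = 6, 0.033 at 7, 0.056 at 8 and 0.086 at 9.

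**The case against.** The strongest reply is that the plan quotes its level and power for 21 patients, and at 21 the two tests have the same cut-off, level and power. That stands: at the planned size the choice of test changes no decision.

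The routes to a smaller n can also be discounted. Consenting up to 30 subjects leaves a margin of nine for reaching 21 evaluable. If the trial closes for toxicity, the safety objective has already failed, so a false efficacy claim matters less. The power sentence counts all 21 patients, which suggests that DFS would not be restricted to those in CR. These arguments make a smaller n less likely or less harmful, but none excludes it. The plan sets no minimum, and its DFS definition starts at CR.

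The plan is silent on a continuity correction. With one, only n = 11 and n = 18 exceed 0.05 between 11 and 20, each by less than 0.002. But the 84% does not reproduce with a correction, and silence would leave that choice to the analyst after the data are in.

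The trial is described as Phase I with safety as its first priority (Section 1.0), and DFS will also be estimated by Kaplan–Meier, so the result would not rest on one p-value. That limits the weight of the point.

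A reader might infer that the planned test is invalid outright, or that it generally runs at about twice its stated level. The figures do not support either. The level is held at n = 21 and at 10, 14 and 17. The excess at 11 and 18 is negligible, and the near-doubling to 0.099 is the worst case, at n = 13.

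**Conclusion.** The point holds in a limited form. At n = 21 the level is kept (0.0431) and the only error is the power, which is 80.3% by exact calculation against a stated 84%. Between n = 10 and 20 the true level is materially above 0.05 at six sizes: 12, 13, 15, 16, 19 and 20, at 0.061 to 0.099. Losing a single evaluable subject from the maximum takes it from 0.043 to 0.087.

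This rests on three assumptions: the chi-square test is uncorrected, as the 84% implies; 0.20 and 0.45 refer to one binary endpoint; and one-year status is known for each subject. The documents allow a smaller n but do not show that it is expected, unless DFS is analysed only in subjects who reach CR. The null stated as a CR rate against an alternative stated as a DFS rate, and the unspecified denominator, are separate defects.

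**What to change.** In Section 11.1.2:
- Replace the chi-square test with an exact one-sample binomial test at one-sided 0.05.
- State that with 21 subjects the null is rejected at 8 or more successes, and that for any smaller number the exact rule is applied to the actual n.
- Restate the power at n = 21 as about 80%. Changing only the name of the test would leave the 84% inconsistent with it.

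The costs are a lower quoted power and, if n falls below 21, a real loss of power wherever the chi-square test exceeds 0.05. Exact against chi-square, power is 0.75 versus 0.87 at n = 20, 0.63 versus 0.80 at n = 16, and 0.57 versus 0.77 at n = 13. At these three sizes the exact test is conservative, with levels of 0.027 to 0.032. That is the price of keeping the stated error rate.

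The edit does not settle which subjects form the denominator or which endpoint the null refers to. Both need their own correction.
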